## Background and Introduction

---

The evaluation and treatment of coagulopathy in the perioperative setting is critical to patient morbidity and mortality. Historically, the coagulation cascade was evaluated with laboratory studies such as prothrombin time (PT), partial thromboplastin time (aPTT) and platelet count. However, viscoelastic tests such as thromboelastography (TEG®) and rotational thromboelastometry (ROTEM®) have allowed for more specific investigation into clot formation, firmness, strength and lysis. Additionally, thromboelastography can help determine which type of blood product is deficient in this clot formation. This test is commonly used trauma and cardiac surgery, but also has applications in obstetrics, transplantation and critical care. Utilization of thromboelastometry has been shown in some studies to decrease costs and some blood product administration.

Although thromboelastometry can offer valuable information, the biggest challenge of this technology is the ability of clinicians to correctly interpret the data. Especially those practitioners that do not utilize this technology on a regular basis. This may lead to improper administration of blood products which could worsen outcomes.

A novel software was developed at our institution to help clinical providers to interpret rotational thromboelastometry (ROTEM®). There are multiple other thromboelastometry guiding applications currently available including TEG2GO, TEM/TEG Guide, and TICapp, however none have these have been validated with ROTEM.

**Hypothesis:** Our hypothesis is that a novel software program will improve the accuracy of ROTEM interpretation amongst practicing clinicians with a range of experience in ROTEM interpretation. Furthermore, we hypothesize that diagnostic accuracy will improve more for inexperienced clinicians than those with extensive ROTEM experience.

## Purpose and Objectives

---

The purpose of this study is to assess a novel rotational thromboelastometry (ROTEM®) interpretation software to determine whether its use improves the accuracy of clinician interpretation.

## Study Population

---

**Age of Participants:** 18+

**Sample Size:**

At Utah:

All Centers: 100

**Inclusion Criteria:**

Current residents and attending physicians in the Department of Anesthesiology who have a range of experience and exposure to thromboelastography.

**Exclusion Criteria:**

Refusal to consent or no longer an active member of the Department of Anesthesiology.

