**Recruitment/Participant Identification Process:**

Participants within the Department of Anesthesiology will be sent a email describing the study and with the informed consent document as an attachment to the email. Imbedded in the email will be an individual link to an online survey. Participants will be informed that by clicking the link they have consented to participation in the study. The online survey will include questions on duration of practice, clinical subspecialty if any, duration of experience with ROTEM, and perceived expertise in ROTEM. The participants when then be shown a series of ROTEM images and asked to interpret them. This will be followed by a short tutorial on the novel interpretation application. Finally, the participants will be shown a second series of ROTEM images and asked to interpret them now with the use of the novel interpretation application.

The study team will continually review participant enrollment and the degree of experience of the participants. If there appears to be developing a selection biased towards a certain level of experience the study team will actively seek out and recruit potential participants within the Department of Anesthesiology either by sending a further emails, in person, or through advertisement at faculty meeting or other community events.

If a participant elects not to participate in the study, they may inform the study team and no further attempts at recruitment will be made. Information as to who does and who does not participate in the study will not be communicated to the Department Chair, Vice Chairs, or Residency Directors.

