**Procedures:**

- Currently, ROTEM study results for each patient are printed and uploaded into the medical record.
- We will retrospectively review these ROTEM studies, de-identify them, and upload them to a database. This is covered under IRB 00096411
- An online survey will be developed using these de-identified images to test the ability of clinicians to correctly interpret ROTEM studies.
- Participants within the Department of Anesthesiology will be recruited by email with informed consent and a link to the survey.
- If the clinician participants consent to the study, they will open the link to the survey and will be asked a short series of questions on their clinical practice (years of training, type of clinical practice, and familiarity with ROTEM) and then shown 20 ROTEM images in random order.
- For each ROTEM image they will be asked to choose what intervention should be done (do nothing, give FFP, give platelets, etc...)
- After 20 images have been reviewed, an online version of the novel ROTEM App will be displayed in the survey and a brief tutorial will be given to demonstrate how to use it.
- The participant will then be shown 20 more study ROTEMs in random order and asked to interpret these studies in a manner similar to the beginning of the survey.
- Data will be recorded in RedCap
- A reference standard of correct responses will be created using the responses of two members of the study team who are known experts in ROTEM interpretation. This reference standard will be used to determine the sensitivity/specificity of clinician responses before and after the use of the App.

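### Prior exposure to an in-house app is neither excluded nor recorded, so the only baseline is unprotected; the bias may be nil, or several points of accuracy

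*Combined protocol and SAP*

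**What the plan says.** - **Origin of the app.** Background and Introduction: "A novel software was developed at our institution to help clinical providers to interpret rotational thromboelastometry". The same section hypothesises that the app improves accuracy, and that it does so more in inexperienced clinicians.
- **Who may enter.** Inclusion Criteria: "Current residents and attending physicians in the Department of Anesthesiology who have a range of experience and exposure to thromboelastography". Exclusion Criteria, in full: "Refusal to consent or no longer an active member of the Department of Anesthesiology".
- **What is asked at the start.** The Recruitment section lists "questions on duration of practice, clinical subspecialty if any, duration of experience with ROTEM, and perceived expertise in ROTEM". The Procedures section lists "years of training, type of clinical practice, and familiarity with ROTEM". Neither list mentions the app.
- **Sequence.** Participants first interpret 20 images. Then, in the Procedures section: "After 20 images have been reviewed, an online version of the novel ROTEM App will be displayed in the survey". A tutorial and 20 further images follow.
- **Analysis.** The Statistical Methods section compares performance before and after the app, and compares experienced with inexperienced clinicians, in a mixed model. It names no term and no sensitivity analysis for prior exposure.
- **Reference standard.** It comes from two study-team experts (Procedures), described in Statistical Methods as cardiac anesthesiologists.
- **Silence.** The documents do not say whether the app was in use in the department before the study. They also do not say whether aids are barred during the first 20 images, or whether those answers are fixed once the app is displayed.

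**The concern.** The first block of 20 images is the only comparator, so the estimated effect of the app is only as good as the claim that this block shows performance without it. In a department of the institution that built the software, some members may have helped to develop or test it, or may have used it. As the criteria stand, they can enter and their first block counts as unexposed.

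Two results are at stake. Any skill carried over from earlier use raises the first-block score and shrinks the overall gain. If earlier use is also unequal between experience groups, the difference in gain that bears on the second hypothesis is distorted. The planned data record ROTEM experience but not app exposure, so the two explanations could not be separated.

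The reference-standard experts raise a related problem. If they belong to the department, nothing bars them from taking the survey, and they would then be scored against a standard they set themselves.

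**Working it through.** The documents give no accuracy rates, effect size, standard deviation, alpha or power. There is only a total of 100 participants, so there is no figure of the plan's own to reproduce. Every input below except the 100 is an assumption.

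**Overall gain.** Let U be unaided accuracy without prior exposure, A aided accuracy, k the points by which a prior user scores higher unaided, and p the share of prior users. Then

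measured gain = A − [(1 − p)U + p(U + k)] = (A − U) − p·k.

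Assume U = 60, A = 85 and k = 15, so the true gain is 25 points.

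| Prior users, p | Loss p·k | Measured gain |
|---|---|---|
| 0 | 0 | 25 |
| 3 of 100 (developers or testers only) | 0.03 × 15 = 0.45 | 24.55 |
| 20% | 0.20 × 15 = 3 | 22 |

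**Experience contrast.** With equal true gains in both groups, the spurious difference in gain (inexperienced minus experienced) is

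k·(p_exp − p_inexp).

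- Equal exposure, including none: 0 points.
- 3 developers, all in an experienced group assumed to number 50: 15 × 3/50 = +0.9 points.
- 40% of experienced and none of inexperienced: 15 × 0.4 = +6 points, in the hypothesised direction.
- The reverse, none of experienced and 40% of inexperienced: −6 points, against the hypothesis.

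**Other values.** A carry-over of 15 out of 25 points means that 60% of the benefit persists when the app is not in use, which may be too much. Write the measured gain as D(1 − c·p), with D the true gain and c the fraction carried over. Take D = 10 to 20 and c = 0.25 to 1.

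- 30% prior users in both groups: a 20-point gain is measured as 20 × (1 − 0.25 × 0.3) = 18.5 down to 20 × (1 − 0.3) = 14.0. A 10-point gain is measured as 9.25 down to 7.0.
- 30% of experienced and 5% of inexperienced: the spurious difference is D·c·0.25, that is 0.6 to 2.5 points for D = 10 and 1.25 to 5.0 points for D = 20. Swapping the shares reverses the sign.

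**Aided scores.** These formulas hold A fixed. If prior users also score m points higher with the app, the loss becomes p(k − m), and it vanishes when m = k.

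**The case against.** The strongest reply is that the premise of exposure is not in the documents. They say that the app was developed at the institution. They do not say that it was released or piloted, or that this department built it. Calling it novel and planning a tutorial suggests that participants are expected to be new to it. With no prior users the bias is zero. This stands, and it is why the point is conditional.

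A reader might infer that clinicians who work often with ROTEM have already met the app, so that a smaller gain among them would be contamination presented as support for the second hypothesis. No section supports this. Residents could equally be the earlier users, which reverses the sign. Experienced clinicians may also gain less simply because they start higher. For the main comparison, carry-over into the first block works against the study's hypothesis.

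A reader might also infer that exposure could never be identified afterwards, or that participants are able to go back and change first-block answers. Neither follows. The survey is still to be developed, the lists of questions do not claim to be complete, and individual links would let the team identify known developers. Silence on navigation does not show that it is open.

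What remains is that the criteria as written admit developers, testers and the reference-standard experts, and that the plan neither records exposure nor says how it would be handled. The doubt about whether exposure exists is exactly what one question would settle.

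**Conclusion.** The gap is real; its consequence is conditional. Nothing in the plan ensures or checks that the first block is free of app exposure, although it is the sole comparator.

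If the app was not available beforehand, the bias is zero or confined to a few developers and testers, about 0.45 points on the assumption of 3 in 100 with a 15-point carry-over. If it was available, the overall gain could shrink by several points (25 to 22 with 20% prior users). The experience contrast could move by about 0 to 6 points either way, depending on which group used the app more. All of these sizes rest on assumed accuracies, shares and carry-over, and on aided accuracy being the same for prior users.

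The documents do not support a conclusion that contamination has occurred or that the second hypothesis is favoured. They do support making the change, because it protects both planned comparisons at almost no cost.

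**What to change.** 1. Add one survey item, before the first image, on prior use of the app or involvement in developing it.
2. Add a line to the exclusion criteria covering app developers, app testers and the two reference-standard experts.
3. Prespecify a sensitivity analysis restricted to app-naive participants, or an adjustment for prior use in the mixed model. The main analysis can keep all eligible participants; making the app-naive the main set is a debatable choice and is not needed to meet the concern.
4. State on the opening page that no aid may be used for the first 20 images, and lock those answers before the app is displayed.

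The cost is one extra question, one survey setting, a few lines of text and the loss of a few participants from the pool. If nobody reports exposure, the study gains documented evidence of a clean baseline.

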**Design**

---

Prospective Biomedical Intervention or Experiment

**Study Procedures**

---

**Recruitment/Participant Identification Process:**

Participants within the Department of Anesthesiology will be sent a email describing the study and with the informed consent document as an attachment to the email. Imbedded in the email will be an individual link to an online survey. Participants will be informed that by clicking the link they have consented to participation in the study. The online survey will include questions on duration of practice, clinical subspecialty if any, duration of experience with ROTEM, and perceived expertise in ROTEM. The participants when then be shown a series of ROTEM images and asked to interpret them. This will be followed by a short tutorial on the novel interpretation application. Finally, the participants will be shown a second series of ROTEM images and asked to interpret them now with the use of the novel interpretation application.

The study team will continually review participant enrollment and the degree of experience of the participants. If there appears to be developing a selection biased towards a certain level of experience the study team will actively seek out and recruit potential participants within the Department of Anesthesiology either by sending a further emails, in person, or through advertisement at faculty meeting or other community events.

If a participant elects not to participate in the study, they may inform the study team and no further attempts at recruitment will be made. Information as to who does and who does not participate in the study will not be communicated to the Department Chair, Vice Chairs, or Residency Directors.

**Informed Consent:**

**Description of location(s) where consent will be obtained:**

Consent will be obtained by email. Resident and attending physicians in the Department of Anesthesiology will be recruited via email. The informed consent document will be attached to the email and participants will be informed that by clicking the link to the online survey, they are consenting to participate in the study.

**Description of the consent process(es), including the timing of consent:**

Consent will be obtained by email. Resident and attending physicians in the Department of Anesthesiology will be recruited via email. The informed consent document will be attached to the email and participants will be informed that by clicking the link to the online survey, they are consenting to participate in the study.

**Procedures:**

- Currently, ROTEM study results for each patient are printed and uploaded into the medical record.
- We will retrospectively review these ROTEM studies, de-identify them, and upload them to a database. This is covered under IRB 00096411
- An online survey will be developed using these de-identified images to test the ability of clinicians to correctly interpret ROTEM studies.
- Participants within the Department of Anesthesiology will be recruited by email with informed consent and a link to the survey.
- If the clinician participants consent to the study, they will open the link to the survey and will be asked a short series of questions on their clinical practice (years of training, type of clinical practice, and familiarity with ROTEM) and then shown 20 ROTEM images in random order.
- For each ROTEM image they will be asked to choose what intervention should be done (do nothing, give FFP, give platelets, etc...)
- After 20 images have been reviewed, an online version of the novel ROTEM App will be displayed in the survey and a brief tutorial will be given to demonstrate how to use it.
- The participant will then be shown 20 more study ROTEMs in random order and asked to interpret these studies in a manner similar to the beginning of the survey.
- Data will be recorded in RedCap
- A reference standard of correct responses will be created using the responses of two members of the study team who are known experts in ROTEM interpretation. This reference standard will be used to determine the sensitivity/specificity of clinician responses before and after the use of the App.

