**Procedures performed for research purposes only:****Statistical Methods, Data Analysis and Interpretation**

---

The sensitivity/specificity and diagnostic accuracy of clinicians will be compared before and after the use of novel ROTEM app. The performance of more experienced clinicians will be

compared to those with little to no experience in ROTEM. Analysis will be done using a mixed effects model to account for clustering of measurements within clinician groups. Inter-rater reliability analysis will be done to assess the similarity within clinician groups using the ICC. The reference standard will be established using two cardiac anesthesiologists with specific expertise in ROTEM analysis. ICC will be used to characterize the inter-rater and intra-rater reliability of these experts to create the reference standard.

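### Image set is not separated from app use: as written, the unaided and app-aided blocks are different series of 20, so set difficulty can pass for app effect

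*Combined protocol and SAP*

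**What the plan says.** The Procedures section describes two blocks. After some questions about their practice, participants are "then shown 20 ROTEM images in random order". Next, "After 20 images have been reviewed, an online version of the novel ROTEM App will be displayed in the survey", with a short tutorial. Then: "The participant will then be shown 20 more study ROTEMs in random order and asked to interpret these studies". The Recruitment section describes the same sequence: "the participants will be shown a second series of ROTEM images and asked to interpret them now with the use of the novel interpretation application".

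In the Statistical Methods section, the main comparison is before against after: "The sensitivity/specificity and diagnostic accuracy of clinicians will be compared before and after the use of novel ROTEM app". On the model, the plan says: "Analysis will be done using a mixed effects model to account for clustering of measurements within clinician groups".

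Randomness is mentioned only for the order of images within each block. The plan does not say how images are allocated to the two blocks, whether all clinicians get the same two sets, or whether the sets are matched on difficulty or reference answer. It mentions no image or set term in the model and no group that reads both sets without the app.

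**The concern.** If the second set happens to be easier, accuracy rises with an app that does nothing. If it is harder, a useful app can look inert or harmful. Shuffling the order inside a block does not change which images the block contains.

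The images come from routine patient records, and the answers range from no action to various blood products, so some spread in difficulty is to be expected. Sensitivity and specificity also depend on which abnormalities each set contains.

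With common sets the difference is shared by every clinician. A larger sample narrows the interval around a quantity that still includes it. At stake is the study's main contrast, which cannot be fully repaired after data collection because image set and condition would coincide.

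**Working it through.** **Inputs from the documents.** Clinicians: "All Centers: 100", taken as 100. Images: 20 per block. The plan gives no power calculation, so it has no figure of its own to reproduce here.

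**Assumed inputs (not in the documents).** Accuracy p of 0.5 to 0.7; between-image SD of accuracy s of 0.05 to 0.20; no app effect; images in the two sets drawn independently from one pool.

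**Step 1: what the contrast measures.** With common sets, aided minus unaided accuracy = app effect + D + sampling error, where D is the difference in mean difficulty between the sets.

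**Step 2: size of D.** SE(D) = s × √(2/20). For s = 0.05, 0.10, 0.15, 0.20 this is 0.016, 0.032, 0.047, 0.063, that is, 95% ranges of about ±3, ±6, ±9 and ±12 percentage points. The number of clinicians is not in the formula.

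**Step 3: what an analysis without an image effect reports.** Naive SE = √[2(p(1−p) − s²)/(100 × 20)]. For p = 0.6 and s = 0.10: √[2(0.24 − 0.01)/2000] = 0.0152. Over the whole grid it is 0.013 to 0.016.

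**Step 4: false-positive rate.** 2 × [1 − Φ(1.96 × SE_naive / SE_total)], where SE_total = √(SE(D)² + SE_naive²). For p = 0.6 and s = 0.10: SE_total = √(0.0316² + 0.0152²) = 0.0351, and the rate is 39.7%.

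| s | False-positive rate, p from 0.5 to 0.7 |
|---|---|
| 0.05 | 17–19% |
| 0.10 | 39–42% |
| 0.15 | 55–59% |
| 0.20 | 66–69% |

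Doubling the clinicians to 200 makes it worse. For p = 0.6 and s = 0.10, the naive SE falls to √(0.46/4000) = 0.0107, SE(D) stays at 0.0316, SE_total is 0.0334, and the rate rises to about 53%.

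A fixed 5-point difference in difficulty gives 0.05/√(2 × 0.24/2000) = 0.05/0.0155 = 3.23 standard errors. It would be declared an app effect about 90% of the time.

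**Step 5: simulation check.** Logistic responses with intercept 0.4 (about 60% accuracy), clinician SD 0.7 logits, 100 clinicians, 40 images, no app or practice effect, 2000 runs per setting, nominal 5%, analysed by paired comparison within clinician.

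| Image-difficulty SD (logits) | SD of set difference (points) | False positives, common sets, no image effect | False positives, sets swapped between random halves |
|---|---|---|---|
| 0.25 | 1.7 | 21% | about 5% |
| 0.5 | 3.3 | 43% | about 5% |
| 1.0 | 5.9 | 65% | about 5% |
| 1.5 | 8.2 | 75% | about 5% |

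Repeat runs differ by a few points. The second column is the set part alone; with clinician and response sampling error added, the SD of the whole estimate is somewhat larger (3.7 rather than 3.3 at image SD 0.5). With the sets swapped, the SD of the whole estimate is about 1.3 to 1.5 points. Drawing for each clinician which 20 of the 40 are unaided gave 5.9%, 3.9% and 5.2% at image SD 0.25, 0.5 and 1.0.

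**Step 6: why swapping works.** In the half with A unaided and B aided, the contrast is app effect + D. In the other half it is app effect − D. The mean of the two halves contains no D.

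**The case against.** **The plan does not say that the sets are fixed.** This is correct. A reader might infer that every clinician certainly gets the same two disjoint sets, but the text is silent on allocation. If each participant's 40 images were split at random between blocks, the problem would disappear. What stands against the objection is that a further 20 images, called a second series in the Recruitment section, most naturally means different images, and no pool or draw is written.

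**A mixed model could absorb it.** In part. The stated clustering is by clinician group and no image effect is mentioned, but the full specification is not given. A reader might infer that the confidence interval must hide the problem; that is so only if image is left out. Treating image as random restores roughly nominal error: a by-image test on the same common sets gave 6.2%, 5.8%, 5.3% and 4.3% at the four image SDs. The price is power: at image SD 1.0, about 33% for a 0.5-logit app effect and 83% for 1.0 logit. It also leaves D in the estimate and relies on both sets being random draws from one pool.

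**It is variance rather than bias.** A reader might infer a systematic bias in a known direction. The documents do not support that: under random selection of images D averages zero over hypothetical repetitions. In the one study actually run, though, D takes a single unknown value shared by all clinicians.

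**The size rests on assumptions.** This is true, and only a zero app effect was examined for false positives. With a large true effect (1.5 logits, about 24 to 26 points), an error of 3 to 6 points would shift the estimate but rarely the conclusion.

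**Conclusion.** The point holds as a gap in the stated design. On the natural reading, image set and app use coincide, so the main before/after contrast includes the set difference. With 100 clinicians, about 60% accuracy and no app or practice effect, an image SD of 0.25 to 1.5 logits gives a set-difference SD of about 1.7 to 8.2 points and about 21% to 75% false positives. Those rates require common sets and an analysis without an image effect; neither is stated outright, and none of the variance inputs is in the documents.

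A reader might also infer that swapping the sets makes the before/after difference a clean app effect. It does not. The app block always follows 20 practice images and a tutorial. With sets swapped and an assumed practice gain of 0.2 logits, a useless app is still declared effective in about 60% to 81% of simulated trials. That is a separate limit on interpretation.

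**What to change.** State in the Procedures section how images are allocated to blocks, and make that allocation random across participants:

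- Split the 40 images once into forms A and B, balanced on reference answer. The reference answers must be settled before the split.
- Randomise each participant's individual survey link 1:1, stratified by ROTEM experience, to A unaided and B aided, or to B unaided and A aided. Alternatively, draw for each participant which 20 of the 40 are read unaided.
- Specify crossed clinician and image (or form) effects in the mixed model.
- State that the app block always comes second, so the before/after difference still includes any effect of practice, fatigue or the tutorial.

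If a per-participant draw is already intended, one sentence saying so settles the allocation, and the model term should still be added. The cost is two survey versions, a short addition to the protocol and one model term. No extra participants, images or reading time are needed, but the change has to be made before the survey goes out.
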